IRB Study Number: 20210017

Mobile delivery of PrEP at a Syringe Services Program—A
Pilot Study

Protocol Version 1.1
Protocol Version Date 04/25/22
eProst ID Number 20210017
PI [name]
NCT Number 04782180

IRB Study Number: 20210017

1) **Protocol Title:** Mobile delivery of PrEP at a Syringe Services Program—A Pilot Study

[figure not shown]
2) **Objectives***

Aim 1: To develop a sustainable protocol for *Rapid Mobile PrEP* initiation at the IDEA Syringe Services Program (SSP).

Aim 2: To assess the acceptability and feasibility of *Rapid Mobile PrEP* for People Who Inject Drugs (PWID) who utilize the Miami IDEA SSP.

3) **Background***

PrEP is an understudied and underutilized HIV prevention strategy for PWID. PrEP has been widely studied in MSM. The evidence for daily oral PrEP is compelling; clinical trials have demonstrated risk reduction of 44-86% in HIV infections for those receiving PrEP with efficacy >90% for those taking the medication more than 4x/week (6-11). The Bangkok Tenofovir Study showed a 48.9% decrease in HIV incidence in PWID who took daily tenofovir compared to those who took placebo, as well as significant interest among PWID in continuing PrEP after the trial. However, there has been a large gap in the literature about PrEP in PWID since that trial. In Miami, our preliminary data from the National HIV Behavioral Surveillance (NHBS) IDU4 cycle showed that of 434 participants, 88.5% would take an HIV prevention pill if it were available to them at no cost. Through our recent CFAR pilot award, we assessed knowledge and interest in PrEP at the IDEA SSP among HIV negative clients (n=159). Of PWID surveyed, 70% were not aware of PrEP. Of those with knowledge about PrEP, 75% were interested in linkage to PrEP and received a referral for PrEP services. However, only 6% made an appointment with a provider to be evaluated for PrEP, and ultimately no one surveyed received a prescription for PrEP. These findings suggest willingness to use PrEP among PWID at the IDEA SSP, yet overwhelming barriers to PrEP use including low PrEP awareness and the same structural and economic barriers that we have documented in MSM populations (cost, transportation, language issues, stigma, and immigration status).

4) **Inclusion and Exclusion Criteria***

Inclusion criteria for this study are: 1) over the age of 18, 2) speak either English or Spanish, 3) ability to provide informed consent, 4) currently enrolled in the SSP and have exchanged at least two times in the past three months, 5) have a negative HIV rapid test result, 6) estimated creatinine clearance > 30 ml/minute for Descovy and >60 for Truvada. Individuals will be excluded from this study if they 1) do not meet the above criteria of inclusion, 2) decline to participate, 3) test positive for HIV via rapid test, 4) are pregnant or plan on becoming pregnant 5) have symptoms acute HIV. *Any other comorbidities that at the discretion of the investigator would prevent the participant from participating in the study.*

5) Study Design

To create a sustainable protocol for dissemination of our *Rapid Mobile PrEP* initiation at future Florida SSP expansion sites (Aim 1):

Firstly, we will develop a protocol for initiation of *Rapid Mobile PrEP* at the Miami IDEA SSP site. Throughout the grant period, we will continuously update our protocol through rapid feedback and implementation of new approaches to overcome encountered problems as they arise. In addition to academic dissemination of our work, we will produce an adaptable protocol for new SSPs as they expand throughout the state. We will enroll a prospective, open-label cohort, similar to the PrEP Demonstration Project at the Miami-Dade County Health Department, assessing uptake, adherence, and retention.

Acceptability and feasibility of *Rapid Mobile PrEP* among SSP clients (Aim 2):

We will pilot test mobile PrEP at the IDEA SSP (N=100), conducting ongoing brief qualitative assessments and process improvement and developing sustainable protocol for adaptation at Florida's SSP expansion sites in geographic hotspots. We will report the proportion of eligible PWID who elect to initiate *Rapid Mobile PrEP* to understand acceptability among at-risk PWID. Likewise, we will report correlates of initiation and retention. We hypothesize that coupling PrEP services with the provision of syringes and harm reduction equipment will increase retention in this *Rapid Mobile PrEP* initiation study.

We will conduct detailed interviews including demographics, drug and sexual risk behaviors, and medical history. Labs will include: HIV via 4th generation test, HBsAg, gonorrhea/chlamydia (urine, rectal, pharyngeal), syphilis, creatinine, and HCV RNA. Participants will be offered immediate FTAf at the IDEA SSP on the first encounter and will meet with the peer navigator for a medication management and adherence plan that may include on-site storage of medications and deliveries of PrEP coupled with provision of injection supplies.

If a participant becomes ineligible for PrEP during follow up based on renal function, other adverse events, or HIV infection, they will be contacted and discontinued from the study. Participants who test positive for HIV during study follow up will be linked to HIV care. Participants with chronic hepatitis B virus infection will be contacted immediately by the clinician for a discussion of the risks and benefits of FTAf in the context of chronic hepatitis B. Finally, PWID who decline study enrollment will be asked to participate in a brief survey that will include demographics, reason for declining, PrEP awareness and knowledge, and perceived HIV risk. Those who decline the study will receive \$25 cash payment for this brief, 30 minute interview.

[figure not shown]
The effectiveness of PrEP requires that it be taken every day minimizing missed doses as well as continuing PrEP over time during periods of potential HIV exposure. Follow up visits will occur at 1, 3, 6, 9 and 12 months. At each study visit participants will complete surveys about PrEP use since their last visit including semiqualitative/open-ended questions about reasons for use or non-use. We will use this combination of quantitative and qualitative data to determine individual and structural contributors to non-adherence and discontinuation of PrEP among PWID. For each study visit including baseline, participants will receive \$50 cash payment.

6) Arms and Interventions

This single arm pilot study will assess the effectiveness of on site initiation of PrEP and followup at an SSP (fixed site or mobile exchange on outreach). The study is 1 year duration, and study visits are conducted at 0, 1, 3, 6, 9 and 12 months as outlined above. The intervention is delivery of PrEP outside of a traditional healthcare clinic. The principal medication offered will be FTAF 200/25mg tablet to be administered orally. In this study, we will offer Descovy to men and trans women due to decreased risk of side effects. If the participant is assigned female at birth, Truvada will be prescribed instead of study drug per FDA approval. **It is noted that significant risk for HIV among PWID is sexual.** The intervention will include wraparound support by the peer navigator. Study visits will be conducted either at the IDEA Exchange fixed location, or on the mobile unit in the community (e.g. homeless encampments). The fixed site and mobile unit are equipped with private rooms for medical encounters. Medical visit with a provider and phlebotomy will be provided on site.

7) Procedures Involved*

Figure 1. Conceptual Framework for *Rapid Mobile PrEP*

8) Primary Endpoints

| Patient-Level Outcomes | Definition | Implementation Construct Domain | Definition |
|--|---|---|--|
| PrEP levels at 6 month follow up (primary) | Intracellular levels of tenofovir diphosphate (TFV-DP) by dried blood spot (DBS). | Acceptability/feasibility of Rapid Initiation of PrEP | Number of PWID at risk for HIV that enter Rapid Mobile PrEP |
| Time to PrEP initiation post negative HIV | Number of days between receiving negative HIV test | Acceptability/feasibility of Rapid Initiation of PrEP | Mean time to PrEP initiation among PWID. |

| | | | |
|------------------------|---|-------------------------|---|
| rapid test (secondary) | result and initiating PrEP, by self-report | | |
| PrEP Persistence | TFV-DP levels on DBS, pill counts, medication log, appointment attendance | Barriers to persistence | Exploration of challenges to PrEP persistence |

9) Data and Specimen Banking*

For clinical data, we will use the UHealth's electronic health record, UChart, which is locked under dual authentication.

All data collected will be housed in the REDCap database system, which is locked under dual authentication by University of Miami Information Technology and then extracted for analysis by the principal investigator. Only study staff will have access to survey results.

As for the in-depth interviews, sessions will be audio-recorded, transcribed by an external company, de-identified for analysis and stored on a password-protected computer in a secured office in the Don Soffer Clinical Research Center. Only study staff will have access to results.

10) Data Management*

Quantitative Data Analysis: Quantitative data will be analyzed using descriptive statistics and frequencies to examine the acceptability and feasibility characteristics of the PWID participants. Categorical data will be analyzed using frequency of responses and continuous variables will be analyzed using means and standard deviations. To assess barriers and facilitators to PrEP initiation (uptake), adherence, and retention, we will use Cox proportional hazard models to identify significant predictors for uptake, adherence, and retention on PrEP, and retention data will be presented as Kaplan-Meier survival plots. Multivariable models will be built to control for age, gender, race/ethnicity, insurance status, and income. Variables of association interest include: self-reported barriers to PrEP, sexual and injection risk behaviors, substance use, and social determinants of health (e.g., homelessness).

All quantitative data will be stored and managed in REDCap and all analyses will be performed using SAS statistical software (Version 9.4; SAS Institute, Cary, NC).

Qualitative Data Analysis: Qualitative data collected from the in-depth interviews will be analyzed using general inductive methodology, which allows for themes to be developed from the raw data based on a study objective/research question. A data codebook will be generated in an iterative process during transcript reading by the study team. All qualitative data analysis will be conducted using Dedoose (version 8.2.14, Sociocultural Research Consultants, Los Angeles, CA), a cross-platform software used for analyzing qualitative and mixed methods research.

IRB Study Number: 20210017

11) Risks to Subjects*

Study procedures: there is risk of discomfort to phlebotomy, but no risk above a routine sexual health visit

Study Drug: Serious risks of taking Truvada and Descovy includes serious drug reactions such as lactic acidosis, hepatomegaly with steatosis, hepatotoxicity, hepatitis B virus exacerbation, pancreatitis, nephrotoxicity, bone density loss, neutropenia, immune reconstitution syndrome, autoimmune disorders and angioedema. Common adverse reactions include diarrhea, headache, fatigue, elevated CK, abnormal dreams, dizziness, insomnia, hypercholesterolemia, hyperamylasemia, neutropenia, LFTs elevated, nausea/vomiting, depression, rash, dyspepsia, abdominal pain, asthenia, increased creatinine, arthralgia/myalgia, cough, paresthesia, peripheral neuropathy, palmar-plantar hyperpigmentation, hypertriglyceridemia, hematuria, hyperglycemia, glycosuria, rhinitis and flatulence.

Risk of HIV acquisition in PWID is extremely complex. This study is to assess the acceptability on on-site initiation of PrEP and persistence over 1 year. Importantly, Descovy is preferred for PrEP due to decreased nephrotoxicity and bone toxicity. However, the initial studies were only in men who have sex with men and transwomen. Therefore, we will prescribe Descovy, the preferred medication to those who meet eligibility i.e. MSM or transwomen. We will prescribe Truvada to cis women while explaining the increased risk of loss of bone mineral density and renal function. Importantly, HIV outbreaks in this country among PWID, including in Miami, and their resultant investigations have all indicated that sexual risk, especially from sex work, plays a major role in HIV acquisition. Therefore we will offer different PrEP medications only because the studies for Descovy have not yet been conducted in women.

12) Adverse Events and Serious Adverse Events

AEs will be any of the common adverse reactions defined above. SAEs will include any hospitalization or death or disability that occurs with participants in the trial. AEs will be reported to the IRB in continuing reviews. SAEs will be reported to the IRB within 24 hours.

The following AEs of interest will be collected and reported: lactic acidosis, hepatomegaly with steatosis, hepatotoxicity, hepatitis B virus exacerbation, pancreatitis, nephrotoxicity, neutropenia, immune reconstitution syndrome, autoimmune disorders and angioedema.

13) Potential Benefits to Subjects*

The potential benefit to the PWID is that they will be able to access rapid on-site PrEP initiation with few barriers, improving their overall health in the short and long term.

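### HIV infection during follow-up is foreseen and acted on, but no outcome, analysis or safety definition in the plan calls for it to be reported

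*Combined protocol and SAP*

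**What the plan says.** Section 5 includes HIV testing among the study labs: "Labs will include: HIV via 4th generation test, HBsAg, gonorrhea/chlamydia (urine, rectal, pharyngeal), syphilis, creatinine, and HCV RNA". For a participant who becomes ineligible during follow-up "based on renal function, other adverse events, or HIV infection, they will be contacted and discontinued from the study". For those infected it adds: "Participants who test positive for HIV during study follow up will be linked to HIV care".

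Section 8 lists three patient-level outcomes. The primary is the intracellular tenofovir diphosphate (TFV-DP) level at 6 months. The secondary is time to initiation ("Number of days between receiving negative HIV test" result and starting PrEP). The third is persistence, measured by "TFV-DP levels on DBS, pill counts, medication log, appointment attendance". The implementation outcomes are the number entering, the mean time to initiation, and barriers to persistence. Section 10 plans descriptive statistics, Cox models for uptake, adherence and retention, and Kaplan-Meier plots for retention.

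Section 12 sets the safety definitions: "AEs will be any of the common adverse reactions defined above", and "SAEs will include any hospitalization or death or disability that occurs with participants in the trial". It also names ten events of interest, all of them drug reactions. Adverse events go to the IRB at continuing review and serious ones within 24 hours.

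**The concern.** HIV infection is the event that PrEP is taken to prevent, and the plan has a procedure for finding it and responding to it. The same plan gives it no place among the results. If the stated definitions are followed literally, a breakthrough infection in someone prescribed PrEP lies outside the planned outcomes. It also lies outside IRB safety reporting unless that person is hospitalized, dies or is disabled.

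Two planned analyses are also affected. A participant discontinued for HIV before month 6 has no primary drug-level result. If infections occur mainly in people with low levels, their absence makes the summary of the remaining levels look better. And Section 10 does not say whether discontinuation for HIV is an event or a censoring time in the retention curve. Aim 1 is a delivery protocol for other syringe services programs to adapt, and those programs would want to know whether anyone became infected.

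**Working it through.** **Step 1. Where HIV infection could appear.** This is a matter of definitions, so the relevant sections are set side by side.

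| Place | What it covers | HIV infection included? |
|---|---|---|
| Section 5 | Discontinuation and linkage to care | Yes |
| Section 8, patient-level | 6-month TFV-DP, time to initiation, persistence | No |
| Section 8, implementation | Number entering, mean time to initiation, barriers | No |
| Section 10 | Uptake, adherence, retention | No |
| Section 12, AE | Common drug reactions listed in Section 11 | No |
| Section 12, SAE | Hospitalization, death, disability | Only if one of these also occurs |
| Section 12, events of interest | Ten named drug reactions | No |

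Section 5 also names HIV infection separately from other adverse events, so it cannot be read into the AE definition by that route.

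**Step 2. What a descriptive rate would look like.** The plan gives no incidence figure to reproduce. The inputs are N = 100 and 12 months of follow-up (Sections 5 and 6), so at most about 100 person-years (PY). No dropout rate is stated; 75 and 50 PY are assumptions.

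Exact Poisson 95% limits for x infections are:
- lower = χ²(0.025; 2x) / (2 PY), or 0 when x = 0
- upper = χ²(0.975; 2x + 2) / (2 PY), which for x = 0 equals −ln(0.025) / PY = 3.689 / PY

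| PY | 0 infections, per 100 PY | 2 infections, per 100 PY |
|---|---|---|
| 100 | 0 (0 to 3.69) | 2.0 (0.24 to 7.22) |
| 75 (assumed) | 0 (0 to 4.92) | 2.7 (0.32 to 9.63) |
| 50 (assumed) | 0 (0 to 7.38) | 4.0 (0.48 to 14.45) |

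**Step 3. Is an infection likely enough to plan for?** The documents give no incidence for this population, so annual risk r is assumed. The chance of at least one infection among n people followed for a year is 1 − (1 − r)^n.

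| r (assumed) | n = 100 | n = 50 |
|---|---|---|
| 1% | 63% | 40% |
| 2% | 87% | 64% |
| 3% | 95% | 78% |

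**Step 4. Effect on retention.** Suppose 2 of 100 are discontinued for HIV and nobody else leaves. Counted as events, 12-month retention is 98/100 = 98%; censored, it is 100%. If both left before month 6, 2/100 = 2% of the primary results would be missing for this reason. The numerical effect is small, but it depends on a rule that the plan does not state.

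**The case against.** The strongest reply is that the outcomes match the aims. The study is to develop a delivery protocol and assess acceptability and feasibility, and the effectiveness mentioned in Section 6 is that of on-site initiation and follow-up. A single-arm pilot of 100 has no comparator and cannot interpret an incidence rate; the intervals above show it. This stands as far as it goes: leaving HIV infection out as a primary endpoint is not an error. It does not answer the safety-reporting gap, which does not depend on precision.

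A reader might infer that infections will go uncounted, or will show up only as unexplained dropouts. The documents do not support that. HIV infection is a named reason for discontinuation, collected data go into REDCap, and Section 10 plans frequencies for categorical data. A count is therefore recoverable; what is missing is a commitment to report it. Nor was all the text between Section 13 and the recruitment paragraph available for this review, so a further safety or withdrawal provision there cannot be excluded. The outcome, analysis and AE sections were readable.

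A reader might also infer that all the follow-up tests are already scheduled, or that the STI and HCV RNA results should be added to the models as exposure markers. Repeat HIV testing is implied by the reference to positive tests in follow-up, but its timing is not given in the readable text. The lab list stands next to the first-encounter offer of PrEP and may describe baseline only. The Section 10 predictor list is open-ended, so these results are not ruled out of the models. Adding them would load more terms into Cox models that already carry five adjustment covariates and four groups of predictors at N = 100. That addition is not recommended.

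**Conclusion.** The point holds as a reporting gap. In the readable text an infection during follow-up triggers discontinuation and linkage to care but falls under no planned outcome or analysis. It reaches the IRB under the stated definitions only if a hospitalization, death or disability accompanies it. This should be corrected, because a stated rule, not merely a missing detail, leaves out the most relevant adverse result of a PrEP program.

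The statistical yield is modest. No infections in 100 PY would still be compatible with a rate of up to 3.7 per 100 PY, and with up to 4.9 or 7.4 at 75 or 50 PY. The person-years below 100 and the annual risks in the working are assumptions; the conclusion about definitions does not depend on them.

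**What to change.** 1. **Section 8:** add incident HIV infection as a descriptive secondary or safety outcome. Give the number of infections, person-years from first dose to last HIV test, and the rate per 100 PY with exact Poisson 95% CI. List each case with time since last negative test and any available TFV-DP result with its date. The date matters because month 6 is the only drug-level time that Section 8 fixes.
2. **Infection present at baseline:** state a rule and list these cases separately, for example a positive baseline 4th generation test after a negative rapid test. Entry rests on the rapid test and PrEP is offered at the first encounter, so without a rule such cases could be counted as incident.
3. **Section 12:** add HIV infection to the events reported to the IRB.
4. **Section 10:** state whether discontinuation for HIV is an event or is censored in the Kaplan-Meier retention analysis, and report how many participants lack the 6-month TFV-DP result for this reason.

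The cost is protocol and SAP wording and one small table and listing. The limits should be printed with the result: the rate is imprecise, infections after loss to follow-up are unseen, and without a comparator it says nothing about efficacy.

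### The decliner survey does not list the risk-behaviour predictors planned for initiation, so as listed they cannot be compared between people who start PrEP and people who decline.

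*Combined protocol and SAP*

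**What the plan says.** Section 10 (Data Management) commits to one model family for three outcomes: "we will use Cox proportional hazard models to identify significant predictors for uptake, adherence, and retention on PrEP". It adjusts for age, gender, race or ethnicity, insurance and income. The predictors of interest are self-reported barriers, sexual and injection risk, substance use and social determinants such as homelessness.

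Section 5 (Study Design, Aim 2) uses eligible clients as the denominator for initiation and then promises its correlates. On people who say no, it states that "PWID who decline study enrollment will be asked to participate" in a short paid survey. The listed domains are demographics, the reason for declining, awareness and knowledge of PrEP, and perceived HIV risk. Enrolled people get a longer interview that covers drug and sexual risk. The Local Number of Subjects section sets 50 decliners and describes their reasons for refusing treatment, whereas Section 5 speaks of refusing the study.

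Section 8 gives uptake a time variable ("Number of days between receiving negative HIV test" result and starting PrEP). The primary outcome is a drug level at a single visit, month 6. Persistence is a list of four measures: "TFV-DP levels on DBS, pill counts, medication log, appointment attendance". Section 5 adds that "At each study visit participants will complete surveys about PrEP use since their last visit", and that the data will be used "to determine individual and structural contributors to non-adherence and discontinuation of PrEP among PWID".

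**The concern.** A correlate of initiation is a contrast between people who start and people who do not, and each predictor must be measured in both groups. The plan names neither the second group nor, if that group is decliners, a survey that lists the main behavioural predictors. If decliners are left out, the analysis describes only who starts after joining a PrEP study. It cannot then say which eligible clients take up PrEP, which is how Aim 2 frames acceptability. Model wording can still be repaired at analysis; a question that was never asked cannot.

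A second gap sits in the same sentence of Section 10. A Cox model needs an event, a time origin and a censoring rule. None is stated for adherence, and no loss event is stated for retention. Without them, the promised findings on non-adherence depend on a coding chosen later.

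**Working it through.** **1. Figures in the plan.** The documents give 100 participants and 50 decliners, with no power, effect size or precision target. There is no stated calculation to reproduce. Every setting below that is not 100, 50 or the visit schedule is an assumption.

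**2. Predictors against data sources (Sections 5 and 10).**

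| Predictor in Section 10 | Enrolled interview | Decliner survey |
|---|---|---|
| Sexual risk | listed | not listed |
| Injection risk, substance use | covered by drug-risk questions | not listed |
| Homelessness | not named; may be under demographics | not named; may be under demographics |
| Self-reported barriers | partly, through visit surveys | partly, through reason for declining |
| Insurance, income (adjusters) | not named; may be under demographics | not named; may be under demographics |

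The clear mismatch is in the first two rows.

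**3. Starters against decliners, if the items are added.** Assume all 100 start and 50 decliners answer, two-sided 5%, 80% power, exact enumeration of a two-proportion test. OR = [p1/(1−p1)] / [p0/(1−p0)], where p0 is the predictor prevalence in decliners.

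- p0 = 20%: detectable p1 = 42.4%; OR = (0.424/0.576)/(0.20/0.80) = 2.9
- p0 = 40%: p1 = 63.6%; OR = (0.636/0.364)/(0.40/0.60) = 2.6
- p0 = 60%: p1 = 81.4%; OR = (0.814/0.186)/(0.60/0.40) = 2.9

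Terms: the five adjusters plus one predictor, at one term each, leave 50/6 = 8.3 decliners per term. Adding barriers, sexual risk, injection risk, substance use and homelessness together makes ten terms, or 50/10 = 5.0.

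**4. Enrolled people only.** PrEP is offered at the first encounter, so non-starters may be few. The same test gives detectable ORs of 4.1 to 4.9 with 20 non-starters in 100, and 6.4 to 8.1 with 10. This discards timing. If days to initiation vary, Schoenfeld's formula gives HR = exp[(1.96 + 0.84)/√(events × 0.25)]. With 80 events this is exp(2.80/4.47) = 1.9, and with 90 it is exp(2.80/4.74) = 1.8, for a predictor split 50/50. If nearly everyone starts on the same day, the times are tied and that advantage largely disappears.

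**5. Mixed refusals.** Suppose prevalence is 60% in starters and 40% in true PrEP refusers (OR = 1.5/0.667 = 2.25), and a fraction q of decliners refused only the study and resemble starters. Decliner prevalence is then (1−q) × 0.4 + q × 0.6.

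- q = 10%: 0.42, OR 2.07
- q = 30%: 0.46, OR 1.76
- q = 50%: 0.50, OR 1.50

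The documents give no basis for choosing q.

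**6. Adherence.** There are two workable definitions.

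- *Month-6 level.* The approximate detectable difference is 2.80/√(n/4), which is 0.89, 0.72 and 0.63 SD for 40, 60 and 80 samples. With a drug term and the noncentral t distribution (n−3 degrees of freedom) it is 0.91, 0.74 and 0.63 SD. This assumes a 50/50 predictor unrelated to drug and no further covariates, so it is optimistic.
- *Time to first non-adherent visit.* Simulation with 50 v 50 people, five visits, a hazard ratio of 2 and no dropout gives power of 74–78% with Efron ties, 75–79% with a discrete-time model and 67–72% with Breslow ties.

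**The case against.** **Decliners may never have been meant as the regression group.** The plan calls their assessment qualitative, and Section 10 speaks of participants. That is fair, and the point is conditional on it. But Section 5 sets initiation against all eligible clients and promises correlates in the next sentence, so the comparison group has to be stated either way.

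**The survey list may not be complete.** It says what the survey will include, which need not be everything. The finding is therefore that the predictors are not listed, not that they will certainly go unasked. Likewise, the reason for declining may already show whether the study or PrEP was refused; at most a coded category is missing.

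**A reader might infer that Cox cannot be used for uptake.** Section 8 supplies an event and a time, so it can run in enrolled people. The odds ratios in step 4 ignore timing and show the unfavourable case.

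**A reader might infer that Cox is the wrong model for adherence and would cost severe power.** Power as low as 3% and no higher than 61% can be produced, against 73–77% for a two-proportion test. It requires adherence to be dichotomised at one common time, with Breslow ties and an unfavourable event coding. The plan states none of these. The repeated visits, pill counts and medication log could support a proper time to first non-adherence. The defect is a missing definition, and a month-6 regression with an unstated cut-off would share it.

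**Conclusion.** The point holds for initiation. As listed, the decliner survey does not support estimating the association of sexual risk, injection risk or substance use with initiation among eligible clients. Enrolled people alone answer the narrower question of starting after joining. With the items added, the comparison detects odds ratios of about 2.6 to 2.9, assuming 100 starters, 50 decliners, prevalence of 20–60% in decliners and no adjustment. That is enough for strong correlates only.

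The adherence and retention point is secondary: definitions are missing, and more than one model would serve once they are given. These are secondary analyses in a single-arm pilot, and nothing here affects the descriptive month-6 drug-level result. The change is worth making because it is cheap and the missing data cannot be recovered afterwards.

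**What to change.** **Initiation.**
- State in Section 10 who the non-initiators are and where enrolled non-starters fall.
- Add to the decliner interview the same few closed items on sexual risk, injection risk, substance use and housing that enrolled people answer. Add insurance and income if demographics does not already cover them.
- Code whether each person refused the study, PrEP or both.
- Tally everyone eligible who is offered PrEP, because a fixed 50 decliners cannot supply the denominator.
- Compare initiators with decliners by logistic regression with few terms, for example one predictor with age and gender, and report estimates with intervals. Decliners have a single interview and no follow-up time, so Cox does not suit this contrast. Cox on days to initiation can stay for enrolled people.

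**Adherence and retention.**
- Define the retention event and its censoring; Cox and Kaplan-Meier can then stay.
- For adherence, choose one of two acceptable routes. The first is linear regression of the month-6 level, on a log or within-drug scale with a drug term, and with rules for missing samples and levels below the assay limit. Drug follows sex at birth ("If the participant is assigned female at birth, Truvada will be prescribed instead of study drug per FDA approval"), so the gender term should not be read as adherence, and the plan should say whether both terms stay in the model. The second is time to first non-adherent visit, with event, origin and censoring defined and ties handled by Efron or a discrete-time model.

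**Cost.** Wording in Section 10, a slightly longer interview that is already scheduled for 30 minutes and paid, and tally work for staff. Power remains modest.
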